13. STATISTICS

A full description of the statistical analyses to be performed at study completion will be provided in a Statistical Analysis Plan (SAP) prior to unblinding.

Baseline will be defined as those values recorded closest to, but prior to administration of the first dose of study drug.

Unless otherwise noted, significance tests of treatment differences will be tested at the two-sided 0.05 level.

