### **3. OVERALL STUDY DESIGN AND PLAN**

This is a Phase 3, 12-week, randomized, multicenter, double-blind, placebo-controlled, fixed dose study that will investigate the efficacy and safety of TNX-102 SL 5.6 mg taken daily at bedtime for the management of PTSD. This study is to be conducted at approximately 30 investigational sites in the United States.

The total duration of this study over 6 visits will be approximately 13-17 weeks, with 12 weeks of treatment duration and a variable length of screening. This study will consist of a Screening visit (Visit 1, Days -21 to -7), Randomization visit (Visit 2, Day 1), telephone visit (Visit 3, Week 2) and three monthly in-clinic visits (Visits 4, 5 and 6 at Weeks 4, 8, and 12, respectively).

Eligible participants who provide written informed consent to participate will have study assessments performed at Screening, including counseling regarding any required washout and instructions to refrain from use of excluded medications throughout the study.

The length of the pre-randomization screening period is variable (7 to 21 days) in order to accomplish wash-out of previous medications, where appropriate, and allow for return of clinical laboratory results necessary to confirm eligibility. If additional screening time is required, medical monitor approval must be granted for any extensions of the screening interval. At Visit 2, participants will return to the site for additional baseline assessments and randomization (Day 1), when, if they meet all study randomization criteria, they will be randomly assigned in a 1:1 ratio to receive placebo or TNX-102 SL 5.6 mg. A dynamic randomization procedure will be employed at Visit 2 to minimize trial-wide imbalances between the treatment groups for site and sex.

Participants will take the study drug sublingually daily at bedtime, starting on the day that they are randomized and continuing for 12 weeks. Participants will return to the study center for safety and efficacy assessments at Weeks 4, 8, and 12 (or early termination [ET]).

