## 4. ANALYSIS AND REPORTING

### 4.1 Interim Analysis

An interim analysis will be performed when approximately 50% of the initially planned enrollment is evaluable for efficacy assessments. This interim analysis will be performed by an unblinded team separate from the team responsible for the conduct and analysis of the study. An Independent Data Monitoring Committee (IDMC) will review the data and recommend to the Sponsor to increase the sample size by a fixed amount, keep the current sample size and continue, or stop the study early for futility in the event the conditional power is <20%. If the IDMC recommends an increase in sample size, the maximum increase will be limited to 120 additional participants in blocks of 10 participants. If the conditional power is at or over 85% with the current sample size, then the IDMC will recommend continuing at the current sample size; if it is between 20% and <85%, the IDMC will recommend increasing the sample size. The increase will be chosen with the goal of increasing the sample size by the minimum number of subjects sufficient to raise the conditional power to at least 90%. If the conditional power at the current sample size is over 20% and the maximum increase of 120 subjects falls short of raising the conditional power to at least 90%, the committee will recommend an increase of 120 subjects. No further information will be provided to the sponsor beyond this recommendation.

The interim analysis will be conducted approximately 16 weeks after randomization of approximately 125 participants, i.e. when approximately 50% of the initially planned participant enrollment (250) is evaluable for efficacy assessments (approximately 12 weeks); and related data cleaning, database freeze, and administrative tasks have been completed on this cohort (approximately 4 weeks).

In case the study is stopped early for futility, participants will be managed according to a study termination plan.

In the case of an early stop for futility, initial results may be released prior to full database lock; however, clinical study report (CSR) results will be based on the final analysis described below.

Conditional power will be calculated using the following formula ([Mehta, 2010](#)):

$$CP(Z_1, \check{n}_2) = 1 - \Phi \left( \frac{Z_{\alpha} \sqrt{n_2} - Z_1 \sqrt{n_1}}{\sqrt{\check{n}_2}} - \frac{Z_1 \sqrt{\check{n}_2}}{\sqrt{n_1}} \right)$$

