## 5. SAMPLE SIZE DETERMINATION

The study is planned to enroll approximately 250 patients total in a 1:1 randomization, that is, 125 patients in each of the TNX-102 SL 5.6 mg and placebo arms. [REDACTED]

The interim analysis will re-evaluate these assumptions and the IDMC may recommend a sample size increase.

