A Mixed Model Repeated Measures (MMRM) analysis will be performed for the change from baseline in CAPS-5 total score to estimate the treatment difference at Week 12. The model will include all participants in the mITT population, and the dependent variable will be the observed change from baseline in CAPS-5 total score at each post-randomization visit. Covariates in the model will include the fixed categorical effects of treatment, site, sex, and treatment by visit interaction, as well as the continuous fixed covariates of baseline score and baseline score by visit interaction. An unstructured covariance matrix will be used to model the within-subject variance-covariance errors. The Kenward-Roger approximation will be used to estimate the denominator degrees of freedom. Should the unstructured model fail to converge, an autoregressive AR(1) covariance structure will be attempted, then finally compound symmetric should AR(1) not converge.

Missing data for participants in the mITT population will be imputed via multiple imputation (MI) ([Carpenter, 2013](#); [Mallinckrodt, 2013](#)). Ten repeats of the imputation will be performed using Markov Chain Monte Carlo (MCMC) assuming non-monotone missing. Where the study medication was discontinued due to lack of efficacy, lost to follow-up, or to an AE, missing values will be imputed drawing from the baseline values, conditioned on the non-missing post-baseline values, of all participants in the mITT population under the assumption that they are missing not at random (MNAR); covariates will include site and sex. If the study medication was discontinued for any other reason, values will be imputed within treatment group using MI under the assumption that they are missing at random (MAR) with covariates for site, sex, and the CAPS-5 score recorded at each time point (including baseline). The MAR approach will also be applied for sporadic missing values (prior to discontinuation).

The test statistic based upon the least squares (LS) mean treatment difference and associated p-value [REDACTED] will be presented for each stage.

In addition, the least squares means and 95% confidence intervals (CIs) will be calculated for the treatment difference between TNX-102 SL and placebo at each time point.

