## 9.2 Secondary Efficacy Analysis

### 9.2.1 Continuous outcomes

The analyses of continuous secondary endpoints will be analyzed using an MMRM model identical to the primary endpoint, however, there will be no multiple imputation applied. These endpoints will include:

- CGI-S score.
- Change from baseline in SDS total.
- Change from baseline in participants' quality of sleep using the PROMIS Sleep Disturbance scale T-scores.
- CGI-I score
- Change from baseline in the disruption of work/school activities assessed using the SDS.
- Change from baseline in disruption of social life/ leisure activities assessed using the SDS.
- Change from baseline in the disruption of family life/home responsibilities assessed using the SDS.
- Change from baseline in CAPS-5 Arousal and Reactivity (Criterion E).
- Change from baseline in CAPS-5 Intrusion symptoms (Criterion B).
- Change from baseline in CAPS-5 Negative Cognition and Mood (Criterion D).
- Change from baseline in CAPS-5 Persistent Avoidance (Criterion C).
- Change from baseline in CAPS-5 Sleep Disturbance (item E-6).
- Mean PGIC score

- Change from baseline in CAPS-5 Reckless or Self-Destructive Behavior (item E-2).
- Changes from baseline in patient-rated Changes in Sexual Functioning Questionnaire Short-Form (CSFQ-14) in males and in females, analyzed separately
- Change from baseline in MADRS score.

The model will be changed to include the corresponding baseline value of the secondary endpoints instead of baseline CAPS-5. Randomized participants who have a baseline and at least one post-baseline assessment for the endpoint being analyzed will be included in the model. To estimate the difference between the treatment arms in CGI-I and PGIC scores (which do not have baseline assessments), the same method will be used, however, with the observed baseline response and associated interactions removed from the list of covariates. All visits will be included in the analysis. P-values from these comparisons will be considered nominal (conclusions from the sequential testing algorithm will be reported separately).

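### If the unstructured MMRM fails to converge, both named fallbacks assume equal variance at Weeks 4, 8 and 12 and can misstate the Week 12 standard error in either direction

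*SAP*

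**What the plan says.** The primary model in SAP 9.1.1 starts from the most general structure: "An unstructured covariance matrix will be used to model the within-subject variance-covariance errors". Inference uses Kenward-Roger: "The Kenward-Roger approximation will be used to estimate the denominator degrees of freedom". The fallback rule is: "Should the unstructured model fail to converge, an autoregressive AR(1) covariance structure will be attempted, then finally compound symmetric should AR(1) not converge". Neither fallback is described as heterogeneous, and no empirical (sandwich) standard error is named.

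The repeated measures come from "three monthly in-clinic visits (Visits 4, 5 and 6 at Weeks 4, 8, and 12, respectively". The primary test is at Week 12 only. Each stage is fitted separately to multiply imputed data, and the stage statistics are combined with fixed weights of √0.5.

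The rule reaches beyond the primary. The two imputation-based sensitivity analyses and the MAR model in SAP 9.1.2 repeat the primary model. Under SAP 9.2.1 the continuous secondaries "will be analyzed using an MMRM model identical to the primary endpoint", but without multiple imputation. The three key secondaries are among them.

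**The concern.** An unstructured matrix for three visits has six parameters: three variances and three covariances. AR(1) and compound symmetry have two each: one variance and one correlation. The plan therefore gives up visit-specific variances at the first step down, and the second step does not restore them.

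The test is at one visit. If the model pools the variance over three visits, the standard error at Week 12 reflects the pooled value and not the variance at Week 12. Kenward-Roger adjusts for small samples under the assumed structure; it does not repair a wrong one.

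At stake is the validity of the Week 12 test in the one situation for which the rule exists. A standard error that is too small gives a type I error above nominal; one that is too large costs power. The stage 1 Z value also enters the conditional power formula in SAP 4.1, so the interim recommendation would shift with it.

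**Working it through.** **Inputs from the documents**
- Three post-baseline visits (SAP 3).
- Level: "significance tests of treatment differences will be tested at the two-sided 0.05 level" (Protocol 13). The level that applies after a sample size increase is redacted.
- Size: "The study is planned to enroll approximately 250 patients total in a 1:1 randomization, that is, 125 patients in each of the" two arms (SAP 5). Stage 1: "The interim analysis will be conducted approximately 16 weeks after randomization of approximately 125 participants" (SAP 4.1), which leaves about 125 for stage 2.

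**The plan's own figures.** The sample size of 250 cannot be recomputed, because its assumptions are redacted. The stage weight can be: √(125/250) = 0.7071, which matches √0.5. The SAP gives no variance, standard error or type I error for the fallback.

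**Assumed inputs.** All SDs by visit below are assumptions, because the visible text gives none.

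**Step 1, standard error ratio.** With data complete at every visit, a common-variance model uses roughly the mean of the three visit variances in the Week 12 standard error. Modelled over true standard error is

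r = √[ (σ₄² + σ₈² + σ₁₂²) / (3σ₁₂²) ].

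So r < 1 exactly when σ₁₂² exceeds (σ₄² + σ₈²)/2, and r > 1 when it is smaller.

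**Step 2, type I error.** A nominal Z then has null SD 1/r. If both stages use the fallback, the combined statistic has variance 0.5/r² + 0.5/r² = 1/r², so α = 2[1 − Φ(1.96r)]. If only one stage uses it, the variance is 0.5/r² + 0.5 and α = 2[1 − Φ(1.96/√(0.5/r² + 0.5))].

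Worked case, Week 4/Week 8 SDs at 70/85% of Week 12: r² = (0.49 + 0.7225 + 1)/3 = 0.7375, so r = 0.859. Both stages: 1.96 × 0.859 = 1.683, α = 9.2%. One stage: 0.5/0.7375 + 0.5 = 1.178; 1.96/√1.178 = 1.806, α = 7.1%.

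| Week 4 / Week 8 SD, % of Week 12 SD | r | α, both stages | α, one stage |
|---|---|---|---|
| 70 / 85 | 0.859 | 9.2% | 7.1% |
| 80 / 90 | 0.904 | 7.6% | 6.3% |
| 90 / 95 | 0.951 | 6.2% | 5.6% |
| 100 / 100 | 1.000 | 5.0% | 5.0% |
| 110 / 105 | 1.051 | 3.9% | 4.5% |
| 120 / 110 | 1.103 | 3.1% | 4.0% |
| 140 / 120 | 1.211 | 1.8% | 3.3% |

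**Step 3, simulation check.** REML fits were run on null data with 125 patients per stage, 25 sites, sex and baseline by visit, and the two stages were combined with weights √0.5. There were 1,000 trials per row, so the Monte Carlo standard error near 5% is √(0.05 × 0.95/1000) = 0.7 percentage points. Approximate degrees of freedom stood in for Kenward-Roger.

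| SD at Weeks 4/8/12 | Unstructured | AR(1) | Compound symmetry |
|---|---|---|---|
| 10/12/14 | 4.5% | 8.1% | 8.0% |
| 11/12/13 | 5.0% | 6.1% | 5.8% |
| 12/12/12 | 4.0% | 4.2% | 3.8% |
| 14/12/10 | 4.7% | 2.3% | 2.5% |

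For 10/12/14 the modelled standard error was 0.873 of the empirical one under both fallbacks, against 0.865 from the formula. The simulation agrees in direction and is somewhat milder than the formula at both extremes. The unstructured model stayed at 4.0% to 5.0% throughout.

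**The case against.** **The trigger is remote.** The primary fits six covariance parameters to completed three-visit data on about 125 patients per stage. That should rarely fail. This stands, and it is why the severity is low. Failure is somewhat more plausible in the MAR model and the secondaries, which have no imputation, but the complete-data formula carries over to those only approximately.

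**The direction is not fixed.** A reader might infer that the fallback always inflates type I error, because change scores often spread out over time. The documents do not support that: they give no variances by visit, and equal or falling SDs give 5% or less.

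**Imputation does not settle the direction.** A reader might also infer that the SAP's baseline-type imputation inflates type I error by itself, by mixing values near no change with improved patients at Week 12. It does raise the Week 12 spread a little. In a simulation of 3,000 trials per setting, with equal observed SDs of 11 and 15% or 25% dropout by Week 12 (assumed), the Week 12 SD rose to 11.5 to 11.6. After pooling by Rubin's rules, however, the common-variance test rejected in 4.8% to 4.9% of null trials. Only some dropouts get such values under SAP 9.1.1, and those values are conditioned on observed post-baseline scores. That inference should not be drawn.

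**Scope.** CSFQ-14 is scheduled only at Baseline and Week 12/ET (SAP 10.7), so the point does not bear on it. It concerns secondaries with repeated post-baseline visits.

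**A fallback list should end in something simple.** This stands too. Heterogeneous Toeplitz has five parameters at three visits, one fewer than unstructured, and may fail where unstructured fails. A list that stopped at heterogeneous structures could leave no prespecified model.

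**Conclusion.** The point holds in conditional form. If a fallback is used, it imposes one variance across Weeks 4, 8 and 12, and the Week 12 standard error is wrong unless the Week 12 variance happens to equal the average of the other two. With both stages on the fallback and a two-sided 5% level, type I error is about 6% to 9% for SDs rising over the range shown, 5% for equal SDs, and about 2% to 4% for falling SDs. If only one stage uses it, the rising range is 5.6% to 7.1%. These figures rest on assumed SDs and, for the formula, on data complete at each visit. Severity is low because non-convergence is unlikely. The rule is still worth correcting, since its purpose is to give a sound test when the first model fails.

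**What to change.** In SAP 9.1.1, replace the fallback sentence with this order: unstructured; heterogeneous Toeplitz; heterogeneous AR(1); heterogeneous compound symmetry; then AR(1) and compound symmetry only as the last resort. Use Kenward-Roger throughout. State in SAP 9.2.1 that the same order applies to the continuous secondaries with repeated post-baseline visits. The same edit could say what happens if the unstructured model converges in only some of the ten imputed data sets or in only one stage, on which 9.1.1 is silent.

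The cost is a sentence in the SAP and a covariance option in the code. Heterogeneous AR(1) and heterogeneous compound symmetry have four parameters against two for the current fallbacks, and heterogeneous Toeplitz has five, so a rarely used fallback carries slightly more parameters. Keeping the two simple structures at the end ensures that a prespecified model remains.

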#### 7.1.1.2 Sample Size Increase

In the case of a sample size increase, the same inverse-normal method described in the primary efficacy analysis will be applied to the key secondary analyses to adjust the reported p-value; these will be tested at two-sided [REDACTED] to account for the sample size increase.

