#### 9.1.1 Primary Efficacy Analysis

An adaptive group sequential design will be performed for sample size adjustment or futility stop. To assure independence of the stage wise test statistics, the first stage population is defined as all participants available for efficacy analysis in the interim analysis. The second stage population is defined as all participants randomized after the interim cut-off and participants randomized prior to the interim cut-off, who were not available for efficacy analysis in the interim analysis.

Participants that drop out or reach Week 12 by the time of the interim cut-off will be included into the interim analysis. If the study continues until full planned recruitment, participants who were randomized prior to the interim cut-off, but did not drop out or reach Week 12 by the time of the interim cut-off, will be included into the second stage test statistic. Participants that were randomized after the interim cut-off will be included in the calculation of the second stage test statistic. Note that in every case, only participants that meet the mITT population criteria will be included.

Data of different stages will be combined using the inverse normal method to test the null hypotheses that there is no difference in the change from baseline in CAPS-5 total score between TNX-102 SL and placebo treatment groups at Week 12 ([Cui 1999](#)):

$$Z_1 = \Phi^{-1}(1 - p_1)$$

and  $Z_2 = w_1 Z_1 + w_2 \Phi^{-1}(1 - p_2)$

Where:

$Z_1$ = the Z statistic for the first stage

$Z_2$ = the combination test statistic at the end of the second stage

$w_i$ = the weighting applied for each associated Z statistic

$p_1$ = the first stage p-value

$p_2$ =the second stage p-value based on second stage participants

For maximum statistical efficiency, the weights are defined prospectively according to the square-root of the planned proportion of participants in the two stages, relative to the preplanned total enrollment of 250 participants, as  $w_i = \sqrt{0.5}$ . The calculation of these

weights is fixed and will not be changed due to unblinded data and is hence in line with the draft guidance on adaptive design clinical trials ([CDER, CBER, February 2010](#)). In order to control the type-I error, adaptive changes of the stage wise sample sizes will not lead to changes of the weights ([Lehmacher & Wassmer 1999](#)).

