### **14.3 Appendix 3: Seeds for Imputation:**

The following is the list of seeds to be used for any imputations; they will be used in the order that they appear in the production dataset programming first for primary analyses, then secondaries in the order given in this SAP. In the instance that a sample size increase is needed, the post-interim imputations will use a seed that is 10 greater than the one used on the corresponding pre-interim code. If the list below is insufficient for the number of seeds required, the list will repeat with values 1 greater than those given.

549179445

374794564

446287595

823648962

455675309

884575352

293564245

608574838

795925865

935852284

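### Ten imputations leave the primary p-value noisy enough for the seed to decide a borderline trial; 100 or more would cost only computing time

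*SAP*

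**What the plan says.** SAP 9.1.1 sets the number of imputations for the primary analysis: "Ten repeats of the imputation will be performed using Markov Chain Monte Carlo (MCMC) assuming non-monotone missing". Missing values after discontinuation for lack of efficacy, loss to follow-up or an adverse event are drawn from baseline values, conditioned on observed post-baseline scores. Other missing values are imputed within arm as missing at random. No Monte Carlo error target or stability check accompanies the number ten.

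The imputed analysis is used in several places:

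- **Final test.** SAP 9.1.1: "Data of different stages will be combined using the inverse normal method to test the null hypotheses". The weights are fixed at √0.5.
- **Interim.** SAP 9.1.1 defines Z1 as the first-stage statistic, and SAP 4.1 puts the interim Z into the conditional-power formula that decides on futility (below 20%) or a sample size increase (20% to below 85%).
- **Sensitivity analyses.** SAP 9.1.2.1 and 9.1.2.2 both repeat the primary analysis with more dropout reasons treated as missing not at random.
- **Key secondaries.** SAP 7.1.1.1 opens the sequence only if the primary result is significant. The secondaries themselves use no multiple imputation (SAP 9.2.1).

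SAP 14.3 fixes the seeds: "The following is the list of seeds to be used for any imputations". It also fixes their order of use, an offset for post-interim imputations if the sample size is increased, and a rule for extending the list.

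**The concern.** Each imputation is a random draw, and the reported test statistic is built from only ten of them. Running the same code on the same data with another seed gives another z and another p. If that movement is comparable with the distance between the result and the critical value, the seed helps decide the verdict. This trial is described in SAP 1 as pivotal. The seed could affect the primary claim, access to three labelling endpoints and a futility stop, which a later rerun cannot undo.

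**Working it through.** **Inputs**

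- M = 10 imputations (SAP 9.1.1).
- N: "The study is planned to enroll approximately 250 patients total in a 1:1 randomization" (SAP 5), so each arm has 125.
- Weights: "the weights are defined prospectively according to the square-root of the planned proportion of participants in the two stages" (SAP 9.1.1).
- Level: Protocol 13 says that "significance tests of treatment differences will be tested at the two-sided 0.05 level". The SAP's level after a sample size increase (7.1.1.2) is redacted, so two-sided 0.05 (critical value 1.96) is assumed.
- Effect size, SD, power and dropout are not legible. Assumed ranges: fraction of missing information (FMI) 0.05 to 0.40, and Week 12 missingness 10% to 40%.

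**Plan's own figures.** 2 × 125 = 250 and √(125/250) = 0.7071 = √0.5, so size and weights agree. The 250 itself cannot be rebuilt without the redacted inputs.

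**Step 1: formula.** In units of the standard error with unlimited imputations, the pooled estimate varies between seeds with variance FMI/M, and the total variance is inflated by the factor 1 + FMI/M. With equal weights the combined Z has seed variance 0.5s² + 0.5s² = s², the same as one stage, so splitting into stages does not dilute the noise.

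By hand, for an exact p of 0.04 (z = 2.054) and FMI 0.1:

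- M = 10: SD = √(0.1/10) = 0.100; expected z = 2.054/√1.01 = 2.044; (2.044 − 1.960)/0.100 = 0.84, so about 20% of seeds give p > 0.05.
- M = 100: SD = √(0.1/100) = 0.032; expected z = 2.054/√1.001 = 2.053; 0.093/0.032 = 2.9, so about 0.2%.

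**Step 2: Rubin's rules with small-sample df and both stages** (200,000 replicates, exact p = 0.04). Here, exact means with unlimited imputations.

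| FMI | SD of Z, M = 10 | 5–95% of p, M = 10 | p > 0.05, M = 10 | SD of Z, M = 100 | p > 0.05, M = 100 |
|---|---|---|---|---|---|
| 0.1 | 0.10 | 0.027–0.061 | 21% | 0.033 | 0.2% |
| 0.2 | 0.15 | 0.022–0.075 | 32% | 0.048 | 2.8% |
| 0.3 | 0.20 | 0.019–0.089 | 38% | 0.061 | 7.2% |
| 0.4 | 0.23 | 0.016–0.102 | 42% | 0.073 | 11.4% |

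At FMI 0.05 and M = 10, the SD is 0.07 and 11% of seeds cross. At exact p = 0.03, 3% to 25% cross with M = 10 (FMI 0.1 to 0.4) and at most 0.3% with M = 100. At exact p = 0.01, at most 1.2% cross with M = 10.

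**Step 3: patient-level simulations**

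- *250 patients, 65% of dropouts imputed from baseline, ANCOVA at Week 12, 25 datasets per dropout rate with |z| between 1.75 and 2.25, 40 runs of M = 10 each.* At 15%, 25% and 35% dropout the SD of z is 0.070, 0.092 and 0.111, and the minority verdict occurs in 12.6%, 15.4% and 19.1% of seeds. Dividing the SDs by √10 gives 0.022 to 0.035 for M = 100. At z = 2.0 and SD 0.09, 2.0 ± 1.96 × 0.09 = 1.82 to 2.18, or p of 0.07 to 0.03.
- *Baseline-based draws conditioned on observed post-baseline scores, as SAP 9.1.1 requires.* SD 0.076, 0.101 and 0.123 at 15%, 25% and 35% missing; about 0.025 to 0.039 at M = 100; minority verdicts in about 17% to 20% of seeds.
- *Two stages of 125, imputation types mixed 50:50.* At 40% missing (FMI about 0.17, exact p 0.036), M = 10 gives p of 0.020 to 0.068 (5–95%) with 22% of seeds above 0.05; M = 100 gives 0.030 to 0.046 with none above. At 10% missing (same exact p), 2.7% against none.

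**Step 4: interim.** With n1 = 125, n2 = 250 and 125 remaining, the SAP 4.1 formula reduces to CP = 1 − Φ(1.96√2 − 2·Z1) = 1 − Φ(2.772 − 2·Z1). CP = 20% gives Z1 = (2.772 − 0.842)/2 = 0.965. CP = 30% gives (2.772 − 0.524)/2 = 1.124. The two are 0.16 apart. The SD of Z1 at M = 10 and exact CP = 30% is 0.10 to 0.22 (FMI 0.1 to 0.4). A trial with exact CP of 30%, which SAP 4.1 would enlarge, falls below the futility line in 7%, 16%, 22% and 27% of seeds at FMI 0.1, 0.2, 0.3 and 0.4. With M = 100 this is 0% to 1.1%.

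**Step 5: average over all results.** With 80% power, two seed lists disagree on significance in 3.4% to 8.4% of trials at M = 10 and in 1.0% to 2.4% at M = 100 (FMI 0.1 to 0.4).

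**The case against.** The strongest reply is that the plan is valid as written. The seeds and their order are fixed in SAP 14.3, so the result is reproducible and nobody can pick a favourable seed. Rubin's rules account for a finite M, so type I error is not at issue. The loss of efficiency is tiny: at FMI 0.17 the standard error grows by √1.017 − 1, about 0.8%. All of this stands. It does not answer the point, because fixing a seed makes the noise repeatable without making it smaller.

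A second reply is that little may be imputed. The mITT set requires a post-baseline CAPS-5 (SAP 6), and early-termination scores are assigned to the nearest visit (SAP 7.1.2). This also stands. With little missing data, only p-values within about 0.01 of the limit are at risk. The 13% to 20% applies to datasets selected for being borderline; the average over all results is the lower figure in Step 5. The rows for FMI 0.3 and 0.4 are best read as an upper end, since the two-stage simulation reached only about 0.17 at 40% missing.

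Third, the patient-level simulations simplify the planned analysis: ANCOVA at Week 12 in place of the three-visit MMRM, and assumed shares of baseline-based imputation. Three set-ups with different assumptions nevertheless agree on the order of magnitude.

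Finally, M = 100 does not remove the dependence on the seed. It reduces it by about √10 = 3.2.

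**Conclusion.** The concern holds. Over the whole assumed range of missing information, ten imputations leave enough seed-to-seed noise (SD of z about 0.07 to 0.12 at 15% to 35% dropout) to change the verdict of a trial near p = 0.05. The same noise can move an interim result across the futility line if, as SAP 9.1.1 implies, the interim Z comes from the imputed analysis. A clear result is hardly affected. The sizes rest on an assumed dropout rate, an assumed share of baseline-based imputation and a two-sided 0.05 level. This is a minor weakness in precision that can be removed almost entirely at negligible cost.

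**What to change.** In SAP 9.1.1, replace ten with at least 100 imputations. State that the number applies to the primary analysis in both stages, the interim Z1 and the sensitivity analyses in 9.1.2.1 and 9.1.2.2. Keep the seeds in 14.3, whose extension rule already covers any additional ones. If missing information could be high (FMI 0.3 or more), use 200 or add a Monte Carlo error target for the combined Z. With M = 200 and an exact p of 0.04, seeds crossing 0.05 fall to 1.7% at FMI 0.3 and 3.9% at FMI 0.4.

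The change should be a dated SAP revision made before the interim data are unblinded. Protocol 13.4.2 leaves the imputation details to the SAP, so its text need not change. No patients are added and no power is lost. About 48,000 simplified imputed analyses ran in under 40 seconds; the full MMRM will be slower.

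### After a sample-size increase, the planned 95% CI for the primary endpoint is not tied to the weighted test and can disagree with the primary p-value in borderline results

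*SAP*

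**What the plan says.** **Test.** SAP 9.1.1: "Data of different stages will be combined using the inverse normal method". The weights come from the planned stage proportions, "relative to the preplanned total enrollment of 250 participants", which gives sqrt(0.5) for each stage. They stay fixed: "adaptive changes of the stage wise sample sizes will not lead to changes of the weights".

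**Estimate and interval.** The same section fits an MMRM, with all mITT participants in the model, "to estimate the treatment difference at Week 12". The test statistic and p-value are to be shown for each stage. A separate sentence adds that "the least squares means and 95% confidence intervals (CIs) will be calculated for the treatment difference" at each time point. It names no stage weights, combination or adjustment.

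**Key secondaries.** SAP 7.1.1.2 says that after an increase the same inverse-normal method "will be applied to the key secondary analyses to adjust the reported p-value". It mentions no estimate or interval.

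**General statements.** SAP 9.1 says the primary analysis accounts for the interim. Protocol 13.6 says results from before and after the interim are combined by the CHW method and leaves the details to the SAP. Neither defines an estimator or a confidence interval.

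**Interim.** SAP 4.1 places the analysis "approximately 16 weeks after randomization of approximately 125 participants". It allows up to 120 more participants, in blocks of 10, when conditional power is at least 20% and below 85%.

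**The concern.** Fixed weights keep the test valid when the second-stage size depends on first-stage data. An ordinary MMRM on all participants instead weights the stages by the information they actually contribute. With an even split and no increase the two coincide. After an increase they do not, so the trial could report a significant primary p-value beside an interval that includes zero, or the reverse.

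This can only happen near the significance boundary, which is where it would matter most. SAP section 1 calls the study pivotal, and SAP 7.1.1.1 ties the key secondaries to labeling. If test and interval conflicted, choosing an interval after unblinding would look data-driven.

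**Working it through.** **Inputs from the documents.** First stage 125, planned total 250, maximum increase 120 and the conditional-power rule (SAP 4.1); fixed weights (SAP 9.1.1); 1:1 allocation (SAP 3.2). Protocol section 13 says that, unless otherwise noted, "significance tests of treatment differences will be tested at the two-sided 0.05 level".

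**Assumptions.** The SAP's own test level is redacted, so 1.96 is assumed. Effect size and SD are redacted, so effects are in SD units over a range, with positive meaning benefit. The Week 12 contrast is treated as normal; the MMRM and the multiple imputation are not simulated.

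**1. Reproduce the plan's weights.** w = sqrt(125/250) = 0.7071 for each stage, as stated.

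**2. Weights in an ordinary full-data analysis.** With second-stage size m, they are sqrt(125/(125+m)) and sqrt(m/(125+m)).
- No increase (m = 125): 0.707 and 0.707, identical to the test.
- +60 (m = 185): 0.635 and 0.773.
- +120 (m = 245 of 370): 0.581 and 0.814. The correlation with the CHW statistic is 0.7071 × (0.581 + 0.814) = 0.986.

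**3. When an increase occurs.** At 125 of 250, the SAP formula reduces to CP = 1 − Φ(1.96·sqrt(2) − 2·z1). CP = 20% gives z1 = 0.965 and CP = 85% gives z1 = 1.904.

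**4. Two worked cases.** Both z1 values lie in that zone (CP 67% and 28%). With +120, CP is Φ(z1·sqrt(245/125) − (1.96·sqrt(2) − z1)), which gives 86% and 45%. Both stay below the 90% target, so both receive the full 120.

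Stage information is n/4 on the SD scale. The pooled standard error is therefore 1/sqrt(370/4) = 1/9.618. The CHW denominator is 0.7071 × (sqrt(125/4) + sqrt(245/4)) = 9.487.

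| | Case A: z1 = 1.60, z2 = 1.20 | Case B: z1 = 1.10, z2 = 1.65 |
|---|---|---|
| CHW Z = 0.7071(z1 + z2) | 1.980, p = 0.048 | 1.945, p = 0.052 |
| Pooled Z = 0.581·z1 + 0.814·z2 | 1.91 | 1.98 |
| Ordinary 95% CI (SD) | −0.006 to 0.402 | 0.002 to 0.410 |
| CHW-inverted estimate (SD) | 0.209 | 0.205 |
| CHW-inverted 95% CI (SD) | 0.002 to 0.415 | −0.002 to 0.412 |

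In A the test is significant and the ordinary interval includes zero. In B the test is not significant and the ordinary interval excludes zero. The inverted interval agrees with the test both times.

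**5. How often.** Simulation of the SAP 4.1 rule, 4,000,000 trials per effect:

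| Effect (SD) | P(increase) | Disagreement given increase | Disagreement, all trials |
|---|---|---|---|
| 0 | 13.9% | 0.9% | 0.1% |
| 0.20 | 34.5% | 2.3% | 0.8% |
| 0.25 | 36.1% | 2.1% | 0.7% |
| 0.30 | 35.1% | 1.5% | 0.5% |
| 0.35 | 31.8% | 1.0% | 0.3% |
| 0.40 | 26.8% | 0.6% | 0.1% |

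A second set of runs gave 2.4% of increased trials at 0.19 SD and 0.5% at 0.41 SD. About three quarters of disagreements are a significant test with an interval that includes zero. With no increase and a 125/125 split there were none.

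**6. Coverage over all trials.** With the futility rule treated as non-binding, the ordinary interval covers 94.6-94.8% at 0.19-0.41 SD and the inverted interval 95.0%.

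**The case against.** The strongest reply is that the SAP never says the interval is unadjusted. It says the analysis accounts for the interim, the protocol says results are combined by CHW, and parts of SAP 7.1.1.2 and 9.1.1 are redacted. The interval sentence also covers every visit and begins as an addition to the test. SAP 9.2.1 likewise keeps nominal secondary p-values apart from the sequential conclusions. This stands as far as it goes: the pooled reading is an inference from an all-participant MMRM with no weighted interval named. But the visible redactions sit at the test level and the p-value, not in the interval sentence. Whether the interval is pooled or stage-wise, nothing visible ties it to the combined test.

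The second reply is that the effect is small and success rests on the test, not the interval. That is correct, and it sets the priority.

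A reader might also infer that the ordinary estimate is seriously biased once the sample size has been raised. Conditional on an increase, it is off by −8.7% at 0.354 SD (drift 2.8, where drift = effect × sqrt(250)/2) and +11.7% at 0.19 SD (drift 1.5), with conditional coverage of 0.976 and 0.979. These figures reflect selection on z1, and inverting the weighted test does not remove them: bias becomes −10.7% and +14.0%, and coverage 0.985 and 0.989. They are no argument for the change.

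**Conclusion.** The gap is real and small. The visible plan gives no interval tied to the primary test, and after an increase the two can disagree in either direction. The size is about 0.5-2.4% of enlarged trials and 0.1-0.8% of all trials, with a coverage shortfall of 0.2 to 0.4 percentage points at effects of about 0.19-0.41 SD.

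A reader might infer that the false-positive rate is affected. It is not: the weighted test keeps its level (simulated one-sided 0.0250 with futility ignored). This is a matter of estimation and reporting.

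The figures rest on the normal approximation, the assumed 1.96 and a first stage of exactly 125. If the redacted level is not two-sided 0.05, a 95% interval would also differ from the test in level. A slight mismatch can arise without an increase if the actual split is uneven: 110/140 gives a correlation of 0.998 between the two statistics.

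Priority: low, but worth settling before unblinding.

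**What to change.** In SAP 9.1.1, name as primary the estimate and interval that invert the weighted statistic. With d_i the stage-wise LS mean difference at Week 12 and SE_i its standard error:

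- estimate = Σ(w_i/SE_i)·d_i / Σ(w_i/SE_i)
- limits = estimate ± c / Σ(w_i/SE_i), where c is the critical value of the primary test.

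The SAP uses Kenward-Roger degrees of freedom, so this closed form is a large-sample version. Solving for the treatment difference at which the combined statistic equals c, using the stage p-values, makes agreement with the test exact.

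Apply the same rule to the three key secondaries in SAP 7.1.1.2. Keep the pooled MMRM estimate and interval, labelled descriptive. If the sponsor already intends a combined estimate, one sentence saying so would do.

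**Cost.** SAP wording and one calculation from stage-wise models that the plan already requires. The interval widens by about 1.2% on average after an increase: 1/0.986 = 1.014 at +120 and 1/0.995 = 1.005 at +60.
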